### **9.2.2 Unified Dyskinesia Rating Scale (UDysRS) total score**

The UDysRS is a rating instrument designed to assess the core features of dyskinesia in Parkinson's Disease. The UDysRS consists of 4 parts:

- Part I, historical disability with regard to the patient's perceptions of the impact on activities of ADL of on-dyskinesia.
- Part II, historical disability with regard to the patient's perceptions of the impact on ADL of off-dystonia.
- Part III, objective impairment, which assesses severity of dyskinesia, affected body parts, and type of impairment (choreic vs. dystonic).

- Part IV, objective disability, based on an evaluation of Part III activities.

Each item in the UDySRS is scored from 0 to 4, with a possible maximum total score of 104.

The UDySRS assessment will be performed at baseline (Day 1, Visit 2), Day 28 and Day 42 (Visits 6 and 7), see Table 8.1-1, starting approximately 30 minutes after the L-DOPA challenge on these days. The UDySRS (Parts III and IV) will be repeated 3 times after each L-DOPA challenge, 30 minutes apart, and will hence be performed approximately 30, 60 and 90 minutes after each challenge.

The data for all 3 assessments performed at each visit will be entered in the eCRF and the Investigator will highlight which of the assessments, corresponding to the assessment where the patient had most severe dyskinesia, that will be used in the descriptive summaries of data and statistical analyses. However, an additional analysis of only Part III and IV data will be performed using the average of the 3 assessment sessions, instead of the assessment marked as most severe.

UDySRS total score at each visit will be summarized using descriptive statistics. The patients' highest recorded score per UDySRS questionnaire item will be used to calculate total UDySRS score. However, an additional analysis of only Part III data will be performed using the sum of each questionnaire item instead of the highest score. UDySRS total score will be analysed using inferential statistics as described under 9.2.1 above.

The analysis UDySRS total score will be done using data from all Parts as well as using data from Part III and IV only (UDySRS total objective score).

In total, the different analyses outlined above result in the following tables being produced (see section 10.2.3.1 below for more details):

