##### **7.2.1 *Secondary endpoints***

- Change from baseline at the final efficacy clinic visit (Day 42) in the Unified Dyskinesia Rating Scale (UDysRS) total score [Timeframe: Baseline to Day 42]. Patients will be challenged with 150% of their standard L-DOPA dose (maximum L-DOPA dose 250 mg) 30 minutes prior to the first UDysRS assessment.

- Change from baseline in UDysRS total score at Day 28, after a 150% L-DOPA dose challenge.
- Change from baseline in total objective score (Parts III, IV) of the UDysRS at Day 28 and Day 42, after a 150% L-DOPA dose challenge.
- Change from baseline in ON Time Without Troublesome Dyskinesia (ON Without Dyskinesia plus ON With Non-troublesome Dyskinesia) based on a PD Home Dyskinesia Diary.
- Change from baseline in Unified Parkinson's Disease Rating Scale (UPDRS) scores (Part III, motor examination).
- Change from baseline in UPDRS combined scores (Parts I, II, III and IV).
- Clinical Global Impression of Change (CGI-C) in overall PD symptoms
- Change from baseline in dyskinesia scores measured by the Kinesia 360 (Great Lakes Neurotechnologies, Inc) wearable dyskinesia assessment system.

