### 11.3.2 **Unified Dyskinesia Rating Scale (UDysRS)**

The UDysRS is a rating instrument designed to assess the core features of dyskinesia in Parkinson's Disease. The UDysRS consists of 4 parts:

- Part I, historical disability with regard to the patient's perceptions of the impact on activities of ADL of on-dyskinesia.
- Part II, historical disability with regard to the patient's perceptions of the impact on ADL of off-dystonia.
- Part III, objective impairment, which assesses severity of dyskinesia, affected body parts, and type of impairment (choreic vs. dystonic).

- Part IV, objective disability, based on an evaluation of Part III activities.

Each item in the UDysRS is scored from 0 to 4, with a possible maximum total score of 104.

The UDySRS assessment will be performed at baseline (Day 1, Visit 2), Day 28 and Day 42 (Visits 6 and 7), see Table 8.1-1, starting approximately 30 minutes after the L-DOPA challenge on these days. The UDysRS (Parts III and IV) will be repeated 3 times after each L-DOPA challenge, 30 minutes apart, and will hence be performed approximately 30, 60 and 90 minutes after each challenge.

The data for all 3 assessments performed at each visit will be entered in the eCRF and the Investigator will highlight which of the assessments, corresponding to the assessment where the patient had most severe dyskinesia, that will be used in the descriptive summaries of data.

The UDysRS assessments will be videotaped at Visits 2, 6 and 7. The video recordings are planned to be used as a backup to the standard investigator rating; for example, to ensure consistency between assessments in case several assessors are involved, or if other issues arise. It may be possible that all video recordings are assessed by a common central rater..

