**Table 3      UDyRS analyses to be performed**

Table ID	UDySRS Parts	Repeated assessments (30, 60 and 90 minutes respectively)	Questionnaire item data handling method
UD 1	I, II, III and IV	Session marked as most severe by the investigator	Highest score
UD 2	III and IV	Session marked as most severe by the investigator	Highest score
UD 3	III and IV	Average of all sessions	Highest score
UD 4	III	Session marked as most severe by the investigator	Sum of each questionnaire scores
UD 5	III	Average of all sessions	Sum of each questionnaire scores

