### 10.2.3 Secondary endpoint(s)

#### 10.2.3.1 Unified Dyskinesia Rating Scale (UDysRS) total score

**Table UD 1 UDysRS total score for all Parts (Full analysis set)**

Result category	Assessment timepoint		NLX-112 (N=XX)	Placebo (N=XX)	Total (N=XX)
Measured value	[Assessment timepoint 1]	n	xx	xx	xx
		Mean (SD)	x.xx (x.xx)	x.xx (x.xx)	x.xx (x.xx)
		Median (Min, Max)	x.xx (x.x, x.x)	x.xx (x.x, x.x)	x.xx (x.x, x.x)
	[Assessment timepoint 2]	n	xx	xx	xx
		...	...	...	...
Absolute change from baseline	[Assessment timepoint 2]	n	xx	xx	xx
		Mean (SD)	x.xx (x.xx)	x.xx (x.xx)	x.xx (x.xx)
		Median (Min, Max)	x.xx (x.x, x.x)	x.xx (x.x, x.x)	x.xx (x.x, x.x)
	[Assessment timepoint 3]	LMM a p-value	xxxxx b	xxxxx c	xxxxx d
		n	xxxxx	xxxxx	xxxxx
		...	...	...	...
Relative change from baseline (%)	[Assessment timepoint 2]	n	xx	xx	xx
		Mean (SD)	x.xx (x.xx)	x.xx (x.xx)	x.xx (x.xx)
		Median (Min, Max)	x.xx (x.x, x.x)	x.xx (x.x, x.x)	x.xx (x.x, x.x)
	[Assessment timepoint 3]	n	xxxxx	xxxxx	xxxxx
		...	...	...	...

a) Linear mixed model (LMM) with treatment, visit and the interaction treatment\*visit as fixed categorical effects and subject within treatment as a random effect. The baseline value of the dependent variable has been included in the model as a continuous covariate. Kenward-Roger's approximation for degrees of freedom will be used.

b) p-value for the difference between NLX-112 at the assessment timepoint and at baseline.

c) p-value for the difference between placebo at the assessment timepoint and at baseline.

d) p-value for the difference between NLX-112 and placebo absolute change from baseline at the assessment timepoint.

Data based on the Full analysis set. The session marked as most severe for Part III and IV have been used. For Part III, the highest score for each individual questionnaire item has been used. All UDysRS item scores for Part I, II, III and IV have been summarized pre patient and assessment timepoint and used as input data to the table. N: Number of observations. SD: Standard deviation. NC: Not calculated - number of evaluable observations less than 3. NA: Not available - no evaluable observations. SAS program: [PROGRAM NAME].sas. Run by: [USERNAME] YYYY-MM-DDTHH:MM:SS. Data extracted at: YYYY-MM-DDTHH:MM:SS

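### The peak-session UDysRS analyses take the session that the investigator marks as worst, with no rule tying the mark to the three recorded scores, and the total score has no mark-free version

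*SAP*

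**What the plan says.** After each challenge, UDysRS Parts III and IV "will be repeated 3 times after each L-DOPA challenge, 30 minutes apart" (SAP Section 9.2.2; Protocol Section 11.3.2 agrees). Nothing is discarded: "The data for all 3 assessments performed at each visit will be entered in the eCRF". The session to be analysed is then picked by judgement: "the Investigator will highlight which of the assessments, corresponding to the assessment where the patient had most severe dyskinesia".

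The two documents give the mark different reach. In Protocol Section 11.3.2 the marked session is the one "that will be used in the descriptive summaries of data". SAP Section 9.2.2 repeats that sentence and adds the statistical analyses. SAP Table 3 gives the session rule for UD 1 (Parts I to IV), UD 2 (Parts III and IV) and UD 4 (Part III) as "Session marked as most severe by the investigator". The footnote to Table UD 1 confirms it: "The session marked as most severe for Part III and IV have been used".

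The SAP also provides for analyses without the mark: "an additional analysis of only Part III and IV data will be performed using the average of the 3 assessment sessions". These are UD 3 (Parts III and IV) and, in Table 3, UD 5 (Part III). There is no counterpart for the total score.

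The total score is the first secondary endpoint listed in Protocol Section 7.2.1: "Change from baseline at the final efficacy clinic visit (Day 42) in the Unified Dyskinesia Rating Scale (UDysRS) total score". The primary endpoints in Section 7.1.1 are all safety endpoints.

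**The concern.** A worst session can be read directly from the three recorded scores. The plan instead inserts a second judgement between the ratings and the analysed value. Neither document says what happens if the marked session does not have the highest score.

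The mark may not be applied uniformly. The rater may be an independent neurologist or the treating physician, and the same rater is kept only if possible (Protocol Section 11.3). Central reading of the videos is only a possibility (Section 11.3.2). Inconsistent marking adds noise to a comparison of about 16 with 8 patients. If a rater has guessed the allocation, the mark also offers a second route for bias, beside the ratings themselves. The SAP gives the mark more weight than the protocol does, because it now feeds the tests on which SAP Section 5.1 bases any inference of superiority.

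**Working it through.** The documents state no SD, effect size or agreement rate, so there is no figure of theirs to reproduce. I set the passages side by side, then show a range under stated assumptions.

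**1. Which analyses depend on the mark (SAP Table 3)**

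| Table | Parts | Session used | Depends on mark |
|---|---|---|---|
| UD 1 | I to IV | marked | yes, through III and IV only |
| UD 2 | III, IV | marked | yes |
| UD 3 | III, IV | average of three | no |
| UD 4 | III | marked | yes |
| UD 5 | III | average of three | no |

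Parts I and II are not repeated, so the mark reaches UD 1 only through Parts III and IV. The highest-score-per-item rule is a separate column in Table 3. UD 3 combines it with session averaging, so it acts within a session and does not replace the mark.

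**2. Was the wider use of the mark recorded?** SAP Table 2 lists four changes: omission of the safety set, replacement of the chi-square test, replacement of the Wilcoxon tests, and the four-day diary and wearable window. The use of the mark is not among them. Protocol Section 17.6.1 does not say which session its tests use. The SAP therefore fills a gap without recording it; it does not contradict an explicit rule.

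**3. Illustrative shortfall against the true highest session.** Assumptions: three exchangeable normal session scores with within-visit SD s; the mark hits the highest with probability q and otherwise falls at random on one of the other two.

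- Expected highest = 3/(2√π) × s = 0.846s; expected middle = 0; expected lowest = −0.846s.
- Mean gap when mismarked = (0.846 + 1.692)/2 × s = 1.269s.
- Mean shortfall = (1 − q) × 1.269s.

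| q | Shortfall | s = 1 point | s = 2 | s = 4 |
|---|---|---|---|---|
| 90% | 0.127s | 0.13 | 0.25 | 0.51 |
| 75% | 0.317s | 0.32 | 0.63 | 1.27 |
| 50% | 0.635s | 0.63 | 1.27 | 2.54 |

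**4. A more realistic error model.** Close sessions are the easiest to confuse. Suppose the investigator perceives each score with an error SD of 0.25, 0.5, 1 or 2 times s (1,000,000 simulated visits). Agreement is 88.5%, 78.5%, 64.4% and 51.0%, and the mean gap given a mismark is 0.219s, 0.417s, 0.697s and 0.955s. The mean shortfall is the product:

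- 0.115 × 0.219s = 0.025s
- 0.215 × 0.417s = 0.090s
- 0.356 × 0.697s = 0.248s
- 0.490 × 0.955s = 0.468s

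At similar agreement these are smaller than in step 3, by a factor of about five at 90%.

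**5. Noise or bias?** If mismarking is equally frequent at baseline and Day 42 and in both arms, the mean shortfall cancels from the change and from the arm difference. What remains is extra variance. With s = 2, the session-level SD of the analysed score is 1.50 for the true highest session and 1.70, 1.89 or 2.03 at 90, 75 or 50% agreement under step 3. Bias needs unequal marking. For example, 75% agreement in one arm and 90% in the other at Day 42, with equal baselines, gives (0.317 − 0.127)s = 0.190s, that is 0.19, 0.38 or 0.76 points for s = 1, 2 or 4.

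**6. Context.** With 16 and 8 patients and two-sided 5% alpha, 80% power needs a standardised difference of (1.960 + 0.842) × √(1/16 + 1/8) = 1.21 (normal approximation). Avoidable noise is unwelcome at this size.

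**The case against.** The strongest reply is that the SAP already contains the safeguard. UD 3 analyses exactly the component that the mark can affect, without the mark and in the same model. That largely stands, and it rules out any claim that UDysRS depends wholly on the mark. It does not close the gap: UD 3 replaces the peak with an average, so a difference between UD 2 and UD 3 could come from either cause, and the total score has no counterpart.

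It can also be said that the criterion is fixed (most severe dyskinesia), the trial is double-blind until lock, the same rater is preferred and sessions are videotaped. All of this stands. The item scores are themselves investigator ratings, so a programmed choice would not remove rating bias. It removes only the second judgement.

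Three stronger readings are tempting and not supported:

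- A reader might infer that the mark biases the treatment comparison. That would need functional unblinding. It is conceivable: safety assessments precede the challenge (Protocol Section 8.2), and in the earlier dose study drug-related dizziness was 13.2% at 2 mg against 0.9% on placebo (Table 6.1-1). Nothing in the documents shows that it would happen.
- A reader might infer that an unmarked visit would lose its UD 1 score. The SAP has no rule for this, but the eCRF has completeness checks and queries (Protocol Sections 16.1 and 16.3), and nothing suggests that marks would be missing.
- A reader might take 0.85 session SD, the gap between highest and middle, as the error from one mismark. The gap is smaller when close sessions are the ones confused, and sessions at 30, 60 and 90 minutes follow a time course, so they need not be exchangeable.

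**Conclusion.** The point holds as a minor and inexpensive improvement. UD 1, UD 2 and UD 4 rest on a discretionary mark that no rule ties to the recorded scores. The SAP carries the mark into the tests without listing this among its changes, and the total score has no mark-free version.

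The endpoint is the first-listed secondary one. Its tests are exploratory and unadjusted (SAP Section 5.8), and SAP Section 5.1 calls significant findings indicative. It should not be described as the main endpoint of the trial.

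Under intact blinding the effect is mainly added noise. Its size in this trial is unknown, because the figures above rest on assumed session SDs of 1 to 4 points, assumed agreement rates and exchangeable sessions. If mark and maximum always agree, nothing changes.

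**What to change.** Before unblinding:

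- Define the analysed session by program as the one with the highest Part III+IV sum at that visit, using the highest-score item handling of UD 1 and UD 2.
- Use that same session for UD 4, so that its different item handling does not select another one. State a tie rule. Tied sessions give identical UD 1 and UD 2 values, so the rule matters only for UD 4.
- Keep the investigator-marked session as a sensitivity analysis.
- Report disagreements between mark and maximum by arm and visit.
- Record the change in SAP Table 2.

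The cost is one programming rule and one additional sensitivity table, with no new data. The target remains the worst of the three sessions, and analysed values change only where mark and maximum disagree.

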**Table 3      UDyRS analyses to be performed**

Table ID	UDySRS Parts	Repeated assessments (30, 60 and 90 minutes respectively)	Questionnaire item data handling method
UD 1	I, II, III and IV	Session marked as most severe by the investigator	Highest score
UD 2	III and IV	Session marked as most severe by the investigator	Highest score
UD 3	III and IV	Average of all sessions	Highest score
UD 4	III	Session marked as most severe by the investigator	Sum of each questionnaire scores
UD 5	III	Average of all sessions	Sum of each questionnaire scores

### **9.2.3      ON Time Without Troublesome Dyskinesia**

Change from baseline in ON Time Without Troublesome Dyskinesia (ON Without Dyskinesia plus ON With Non-troublesome Dyskinesia) based on a PD Home Dyskinesia Diary will be summarized using descriptive statistics for all assessment time points. In this analysis, the number of records of ON Without Dyskinesia plus ON With Non-troublesome Dyskinesia divided by the number of non-missing awake records (sleeping records are excluded) for all measurements prior to Visit 2 and for all measurements from 4\*24 hours prior to and up until Visit 6 and 7 respectively will be used as input data for each patient respectively. If there is not

at least 8 hours recorded data available for each patient and visit window, the corresponding timepoint is set to missing for the patient. ON Time Without Troublesome Dyskinesia will be analysed using inferential statistics as described under 9.2.1 above.

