## 6.3 Risk/benefit assessment

### 6.3.1 *Potential risks*

In prior clinical studies of NLX-112, the most frequently reported undesirable treatment effects were dizziness, somnolence, headache, nausea, and malaise; these effects are consistent with the pharmacological profile of NLX-112. These effects occurred mostly during the first days of treatment and were most frequent at the highest doses of study drug (i.e.,  $\geq 3.0$  mg/day).

The study of the tolerability and safety of NLX-112 administered as multiple doses after an adaptive dose titration in healthy subjects showed that progressive up-titration, and adjusting dose escalation based on individual tolerability, allowed some healthy men to tolerate 10 mg/day, when administered as 5 mg BID.

Abrupt discontinuation of NLX-112 after multiple daily dosing of 3.0 mg/day or higher was associated with the sporadic occurrence of withdrawal symptoms (mainly nightmare, anxiety, hallucination, and euphoric mood) which were reduced in severity with progressive down-titration.

Undesirable hemodynamic effects (i.e., decrease in blood pressure and postural hypotension) were observed in some elderly subjects.

Thus, based on prior human experience, NLX-112 can be safely administered up to the dose of 3.0 mg/day (1.5 mg BID), with a progressive up-titration to maximize the tolerability of the drug and a down-titration regimen after the fixed dose period to minimize potential withdrawal symptoms.

In cases of accidental overdose, standard supportive measures should be adopted as required. For further information regarding overdosing, refer to Section 11.2.1.17.

Each patient will be provided with a patient information card with information about the patient's participation in a study, see Section 14.4.

The Principal Investigator at the research clinic will ascertain that adequate facilities and procedures are available to handle emergency situations should they occur during the study.

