### 7.3 Exploratory objectives

- To assess the preliminary efficacy of NLX-112 treatment in improving selected non-motor symptoms of PD, including pain, bladder function, sleep function, mood and quality of living with PD.
- To collect blood samples for potential NLX-112 plasma concentration analysis.

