### 11.3.3 ***PD Home Dyskinesia Diary***

A PD Home Dyskinesia Diary (electronic) will be completed by the patients and/or caregiver with concordance in ON time with dyskinesia between study staff and patient. The diary is integrated in the Kinesia 360 wearable dyskinesia assessment system (Section 11.3.6) and is based on the PD Home Diary developed by Hauser et al 2004 [26]. The diary will be used to score 5 different conditions in 30-minute time intervals during 2x24 hours prior to Visit 2, Visit 6 and Visit 7:

- ASLEEP;
- OFF;
- ON (i.e., adequate control of PD symptoms) without dyskinesia;
- ON with non-troublesome dyskinesia;
- ON with troublesome dyskinesia.

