#### 17.6.2 ***ON Time Without Troublesome Dyskinesia***

Change from baseline in ON Time Without Troublesome Dyskinesia (ON Without Dyskinesia plus ON With Non-troublesome Dyskinesia) based on a PD Home Dyskinesia Diary (see Section 11.3.3) will be summarized using descriptive statistics for all assessment time points. A Chi-Square test will be used to assess statistically significant differences between active treatment and placebo for the whole study period.

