**Table ON 1 ON Time Without Troublesome Dyskinesia (Full analysis set)**

Use the same format as for Table UD 1. Add a footnote stating that the sum of records of ON Without Dyskinesia plus ON With Non-troublesome Dyskinesia for the 2\*24 hours measurements prior to each visit has been used as input data for each patient respectively. Produce the table above for PPS as well, providing there is any de facto difference between the analysis sets. If the LMM is performed using transformed data, insert a footnote about this as well. If the LMM approach is dropped in favour of non-parametric tests, update the table and footnotes accordingly.

*10.2.3.3 Unified Parkinson's Disease Rating Scale (UPDRS)*

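### The SAP analyses the diary endpoint as a share of awake time rather than as ON time, without logging the change or planning any summary of good-ON hours or sleep by arm

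*SAP*

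**What the plan says.** Protocol 7.2.1 lists the secondary endpoint as "Change from baseline in ON Time Without Troublesome Dyskinesia (ON Without Dyskinesia plus ON With Non-troublesome Dyskinesia) based on a PD Home Dyskinesia Diary", and Protocol 17.6.2 repeats it. Both name a time; neither mentions an awake denominator. Protocol 11.3.3 describes the instrument: "The diary will be used to score 5 different conditions in 30-minute time intervals during 2x24 hours". ASLEEP is one of the five states, so a complete day has 48 slots, all classified.

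SAP 9.2.3 analyses something else. The two good ON states are counted and "divided by the number of non-missing awake records (sleeping records are excluded". The same section sets a patient's visit to missing unless there is "at least 8 hours recorded data available for each patient and visit window", without saying whether ASLEEP slots count towards that.

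The SAP does not carry the definition through. The Table ON 1 footnote still describes "the sum of records of ON Without Dyskinesia plus ON With Non-troublesome Dyskinesia" over 2\*24 hours. SAP Table 2 logs two changes for this endpoint, the move from a chi-square test to a mixed model and the wider 4\*24 hour window. It does not log the move from time to awake share.

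No summary of ASLEEP time by arm and no hours-based analysis is planned. The diary otherwise appears only as Listing 16.2.6-10.

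**The concern.** The two measures answer different questions. The protocol asks how much good ON time the patient had; the SAP asks what fraction of waking time was good. The denominator of the second is measured after randomisation, and the protocol gives reasons why it might differ by arm.

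- Sleep is itself a target: an exploratory objective is "improving selected non-motor symptoms of PD, including pain, bladder function, sleep function, mood and quality of living with PD".
- Protocol 6.3.1 says of prior studies that "the most frequently reported undesirable treatment effects were dizziness, somnolence, headache, nausea, and malaise". Protocol 6.1.3 lists somnolence among the most frequent Phase 1 events.
- Protocol Table 6.1-1 shows drug-related insomnia in Study CP201 in the NLX-112 groups and none on placebo.

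If patients on one arm sleep through hours that would have been OFF or troublesome, those hours leave the denominator and the score improves. With no sleep summary beside it, a reader of Table ON 1 could not separate that from relief of dyskinesia.

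**Working it through.** The plan states no effect size or power for this endpoint, so there is no figure to reproduce. The check is algebra on the SAP 9.2.3 formula.

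**Inputs.** W is awake hours per day, G is hours of good ON, and h is the hours that change state. The documents give none of these. The only baseline anchor is inclusion criterion 5: at least 90 minutes of troublesome dyskinesia per 24 h. Assumed ranges: W = 14, 16 or 18; G from 4 h to W - 1.5 h; h = 1 to 2 h, limited to the bad time available.

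**Formulas.** The baseline share is G/W.

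- Real relief of h bad hours: (G+h)/W, a gain of h/W.
- h bad hours become sleep: G/(W-h), a gain of G·h/[W(W-h)].
- Credit ratio, the second gain over the first: G/(W-h).

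**Credit ratio at W = 16**

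| G (h) | h = 1 | h = 2 |
|---|---|---|
| 4 | 4/15 = 0.27 | 4/14 = 0.29 |
| 6 | 0.40 | 0.43 |
| 8 | 0.53 | 0.57 |
| 10 | 0.67 | 0.71 |
| 12 | 0.80 | 0.86 |

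The lowest value over the whole range is 4/(18-1) = 0.24. The highest arises at the entry minimum with no OFF time: at W = 16 and G = 14.5, sleeping through all 1.5 h gives 14.5/14.5 = 100%, a ratio of 1.00. That is the same score as a patient whose troublesome time has all become good ON.

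**All directions, at W = 16, G = 8, h = 2**

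| Change | Awake share | Good-ON hours per 24 h |
|---|---|---|
| Real relief | 10/16 - 8/16 = +0.125 | +2.0 |
| Bad time to sleep | 8/14 - 8/16 = +0.071 (1.14 h of a 16 h day) | 0 |
| Good time to sleep | 6/14 - 8/16 = -0.071 (1.14 h) | -2.0 |
| Sleep drawn proportionally | 7/14 - 8/16 = 0 | -1.0 |
| Insomnia spent in good ON | 10/18 - 8/16 = +0.056 | +2.0 |
| Insomnia spent in bad states | 8/18 - 8/16 = -0.056 | 0 |

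The hours column assumes a complete diary. The share's specific fault is the second row. Hours respond more strongly in the third, fourth and fifth rows.

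**Evidence that sleep may differ by arm.** Drug-related insomnia in CP201 was 3/113, 3/114 and 6/117 at 1, 2 and 3 mg/day, together 12/344, against 0/112 on placebo. Somnolence is not listed in that table, and Protocol 6.1.3 says it was seldom seen in Phase II.

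**Blank night slots.** Take a day with 8 h good ON, 8 h bad and 8 h asleep. Scaled as 24 × good/non-missing, the complete day gives 24×8/24 = 8 h. With the night blank it gives 24×8/16 = 12 h, a 4 h artefact. The awake share is 0.50 both times. If at most 4 of 48 slots may be blank and all four are sleep, the artefact falls to 24×16/44 - 8 = 0.73 h.

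**The case against.** The case for leaving the SAP alone has real strength.

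- **Some denominator is needed.** Recording windows and missing slots vary between patients and visits, and the awake share is unaffected by blank nights. Hours scaled to all non-missing slots without a completeness rule could introduce a larger error than they remove. This stands, and it rules out a plain swap of the main analysis.
- **Hours are not free of sleep effects.** Good ON lost to sleep, or gained through insomnia, moves hours more than the share. This stands too: the choice is between two imperfect measures.
- **The evidence for a sleep shift is thin.** Protocol 6.3.1 places the listed effects mostly in the first days of treatment and most often at 3.0 mg/day or above, while this trial stops at 2 mg/day. The insomnia counts are drug-related events only, so all-cause insomnia on placebo is unknown. This stands as to likelihood. It does not supply a way to check.
- **Sleepiness is seen elsewhere.** The Epworth scale is analysed at the same visits, and adverse events are tabulated by titration period. Neither shows how many diary hours moved into or out of ASLEEP, so neither can explain a difference in Table ON 1.
- **The tests are exploratory.** SAP 5.8 makes no multiplicity adjustment and SAP 5.1 calls significant findings indicative. This limits the consequence to interpretation.

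A reader might go further and infer that sedation will be scored here as efficacy, at about half the value of real relief. The documents do not support that. They establish no sleep shift in either direction at this dose, and a ratio near one half follows only from assuming about half of waking time is good ON at baseline.

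**Conclusion.** SAP 9.2.3 changes the endpoint from ON time to a share of awake time, Table 2 does not log it, and the Table ON 1 footnote contradicts it. Bad time that becomes sleep raises the share by G/(W-h) of the credit for real relief, with no good ON time gained. That is about 0.25 to 1.0 for an assumed 14 to 18 h awake and 4 h or more of good ON.

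Whether this will matter in the trial is unknown. It requires sleep to differ by arm and to be drawn disproportionately from good or bad time; proportional sleep leaves the share unchanged. It would also be too strong to conclude that the share is invalid or must give way to hours, since hours carry sleep effects of their own. What the plan lacks is the means to tell these explanations apart. The remedy is inexpensive and worth making, and it affects the reading of one secondary endpoint rather than the primary safety objective.

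**What to change.** Keep the awake share as the main analysis if preferred, and make these changes to the SAP.

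1. In 9.2.3 and Table ON 1, add an analysis of good-ON hours per 24 h with the 9.2.1 model. Use only diary days that meet a pre-stated completeness rule covering night slots, for example at least 44 of 48 slots non-missing. That threshold is an assumption for the sponsor to settle. Apply it identically at baseline, Visit 6 and Visit 7.
2. On the same days, summarise ASLEEP hours per 24 h by arm and visit.
3. Align the Table ON 1 footnote with 9.2.3, for both the quantity and the window, and say whether ASLEEP records count towards the 8-hour minimum.
4. Log the move from time to awake share in Table 2, with its reason.

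No new data are needed, because all five states are already recorded. The cost is SAP wording, two derived variables and a little more analysis. Some incomplete diary days will drop out of the added hours analysis; the share analysis is unaffected.
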